	
Aim 3: To assess the potential effectiveness of maintenance intervention options (a) booster sessions, or b) SMS reminders) compared with no active ongoing support after completion of a group-based memory skills training program.
 
Aim 4: To estimate the potential costs and cost-effectiveness of delivering the maintenance intervention options compared with no active maintenance.

Inclusion Criteria:	Adults aged >18 years with post-stroke memory complaints
Exclusion Criteria:	Neurodegenerative conditions (e.g. dementia), severe mental health conditions, major illness and unlikely to survive up to final follow-up assessment. Current participation in other individual rehabilitation sessions focusing on memory or other cognitive functions.
Planned Participants:	45 (15 per group; 1:1:1 randomisation)
Safety considerations:	Possible risk of participant distress related to assessment and discussion of memory concerns
Funding	Seed grant from the Stroke Foundation awarded to [name], date of acceptance 15 January 2019.

GLOSSARY OF ABBREVIATIONS & TERMS

Abbreviation/Term	Description (using lay language)
Health service sites	The health services participating in the study by referring participants and collecting baseline data from participants. Sites include: Monash Health; Austin Health; Barwon Health; Melbourne Health; Western Health
iVERVE	An electronic automated messaging system designed and developed by [name] et al. (2018) for message-based e-health interventions.
REDCap	A secure web-based database management system.

STUDY SITES

Site	Contact Person	Address	Phone and Email
Monash Health	[name]	Community Rehabilitation Monash Health Cranbourne Victoria	[name] [contact]
La Trobe University*	[name] (Coordinating Principal Investigator) [name] (Research Officer)	School of Psychology and Public Health La Trobe University Bundoora Victoria *Multi-site study administration/coord.	[name] [contact] [contact]
Austin Health	[name]	Austin Hospital, Heidelberg Victoria	[name] [contact]
Barwon Health	[name]	McKellar Centre Community Rehabilitation Centre Geelong Victoria	[name] [contact]
Melbourne Health	[name]	Royal Melbourne Hospital Parkville Victoria	[name] [contact]
Western Health	[name]	Community Based Rehabilitation Sunshine Hospital [name]	[name] [contact]

INTRODUCTION/BACKGROUND INFORMATION

Lay Summary

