made during the memory skills group). Outcome assessments (T1 6-week, T2 12-week, T3 18-week and T4 24-week assessments) will be conducted by an independent assessor masked to group allocation. The trial will be conducted and reported according to best practice guidelines.

[figure not shown]
Study Coordination

Study coordination, including administration and management, will occur at La Trobe University, Bundoora campus.

Sample size

Based on other similar studies, we believe that recruiting 45 participants is possible in the 12-month study period given that memory groups are conducted in parallel across the multiple health service sites. This sample size would be sufficient to detect a small-medium effect size ($d=0.33$), calculated using G-Power, which compares with medium-large effect sizes of booster sessions in previous literature (Lawson et al., under review; Ponsford et al., 2016).

TIMEFRAMES

PARTICIPANT SAFETY AND WITHDRAWAL

Risk Management and Safety

It is possible that some booster condition participants may become distressed when discussing their memory issues and the changes in their life that have occurred as a result of their stroke. Booster sessions will be conducted by highly experienced clinicians in a sensitive and supportive manner and it will be emphasised that no participant is required to share information that they do not wish to disclose. Any distressed participants will be offered separate counselling and support by qualified clinical staff within the relevant health service who are not members of the research team.

Adverse Events and Serious Adverse Events

Consistent with the Statement of Compliance, this study adopts the policies and guidelines for safety monitoring and reporting as per the NHMRC statement on Safety Monitoring and Reporting in Clinical Trials involving Therapeutic Goods (NHMRC, 2016).

Handling of Withdrawals and Replacements

Information collected prior to a participants' withdrawal will be retained, but no further information will be collected. In cases of participant withdrawing before the conclusion of the booster program, or participants being lost to follow-up, recruitment will continue until target sample size is achieved, within the restrictions of the recruitment period.

STATISTICAL ANALYSES

Aim 1 (*Determining acceptability and safety of the two eHealth interventions*):

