- Pairwise comparisons and linear mixed models will be used to explore between-group differences at T3 and T4 in acceptability ratings. Qualitative data will be thematically analysed to extract themes relating to intervention acceptability from participant interviews, using Braun and Clarke's (2006) approach to thematic analysis.

Aim 2 (*Determining whether the trial design is feasible*)

- Descriptive statistics will be calculated for feasibility measures, including rates of recruitment, study completion, and technological issues.

Aim 3 (*Determining an initial estimate of intervention-effectiveness*):

- Pairwise comparisons and linear mixed models will be used to explore between-group differences at each time point in clinical outcomes. The effect size of each maintenance condition, defined as the magnitude of change from T1-T4, will be estimated with Cohen's *d* based on output from regression models.

Aim 4 (*Estimating and comparing costs of booster sessions, SMS/email reminders, and no active maintenance*):

- Resource use data will be converted to costs and the average costs per participant for each intervention arm described and compared. The costs of each program will be accounted for in the determination of total costs and the average cost per participant. The reference year for costs will be 2019. The net cost per participant achieving the maintenance outcome will be estimated against the control group as a measure of potential cost-effectiveness. Various sensitivity analyses will be performed. If effectiveness information is able to be used for health benefit modeling relative to costs, then these will also be described to inform the business case and budget needed for a larger, fully powered Phase III study.

REPORTING OF RESULTS

Study results will be prepared for publishing at the completion of data collection and analysis. Results will be reported according to guidelines outlined by the Consolidated Standards of Reporting Trials (CONSORT) extension for randomised pilot and feasibility trials checklist, and the Template for Interventional Description and Replication (TIDieR) Checklist for describing an intervention. A final report will also be prepared for The Stroke Foundation in compliance with funding requirements.

DATA SECURITY AND HANDLING

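### The sample-size section says 45 participants can detect d = 0.33, which is not true of a between-arm difference with 15 per arm

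*Protocol*

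**What the plan says.** The Study Synopsis plans "45 (15 per group; 1:1:1 randomisation") in three arms: booster sessions, SMS/email reminders and no active maintenance. The Sample size section first says that 45 can be recruited in the 12-month study period. It then adds: "This sample size would be sufficient to detect a small-medium effect size ($d=0.33$), calculated using G-Power". The same sentence goes on to set this figure against larger booster effects reported in earlier studies. It gives no alpha, power, test, number of measurements or correlation.

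For Aim 3, Statistical Analyses says: "Pairwise comparisons and linear mixed models will be used to explore between-group differences at each time point in clinical outcomes". It defines each condition's effect size as its change from T1 to T4. The Hypotheses section predicts an ordering of the arms: boosters best, then reminders, then no maintenance.

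Outcomes are measured at T1 to T4 (6, 12, 18 and 24 weeks). Three measures are also taken at T0, before the memory skills group. The section on randomisation and blinding places randomisation after the T2 assessment.

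**The concern.** The sentence makes a definite statement about what the design can do. The effect it is compared with is that of booster sessions, the hypothesis orders the arms, and the Aim 3 analysis compares groups. The natural reading is therefore that 0.33 is a standardised difference between two arms, and that the expected booster effect exceeds it comfortably.

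If the figure does not apply to that contrast, the only quantitative statement about what the sample size can detect is misleading. The results are meant to supply parameters for a Phase III trial. A reader who believed the figure could take a null between-arm result as evidence against a small-to-medium effect, which the trial could not provide.

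**Working it through.** **Inputs.** From the protocol: 45 participants, three arms, 15 per arm, stated d = 0.33. Assumed, because not stated: two-sided alpha 0.05, power 80%, compound-symmetric correlation r between visits. No attrition is applied; no dropout rate is given and replacement is planned.

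**1. Can 0.33 be reproduced?** Not as a between-arm difference. It does come out of repeated-measures ANOVA set-ups of the G*Power type, with noncentrality λ = f²·N·m/(1 − r) for m measurements and the conversion d = 2f:

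- *Time effect pooled over arms*, m = 5, r = 0.5, f = 0.165: λ = 0.165² × 45 × 5 / 0.5 = 12.25 on 4 and 168 degrees of freedom. Power is 0.799, and 2f = 0.33.
- *Group-by-time interaction* at 80% power: 2f = 0.334 (m = 5, r = 0.6) or 0.335 (m = 3, r = 0.7).

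Neither is a between-arm Cohen's d. The first concerns change over time in all participants together. For the second, f = 0.165 corresponds to a post-randomisation booster-versus-control difference of about 0.70 to 0.86 SD, depending on the number of visits and on where the reminder arm lies.

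**2. Unadjusted pairwise comparison, 15 v 15.** Noncentral t with 28 degrees of freedom and noncentrality d·√(15 × 15/30) = d·√7.5.

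- d = 0.33: noncentrality 0.904, critical value 2.048, power 14.1%.
- d = 0.5: power 26.2%. d = 0.8: power 56.2%.
- 80% power requires noncentrality 2.902, so d = 2.902/√7.5 = 1.06, which is 1.06/0.33 = 3.2 times the stated figure.
- At d = 0.33, 145 per arm gives 79.97% and 146 per arm gives 80.2%, so 146 per arm (438 in three arms).

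More generous simple settings at d = 0.33: one-sided 5%, 22.3%; both active arms pooled against control (30 v 15), 17.5%.

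**3. Baseline-adjusted comparison, 15 v 15.** With p pre-randomisation scores and the mean of q follow-ups, the residual variance as a fraction of the outcome variance is

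v = [1 + (q − 1)r]/q − p·r²/[1 + (p − 1)r],

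and the detectable effect is 1.06·√v. With randomisation after T2, up to two pre-scores (T1, T2) and two follow-ups (T3, T4) are available.

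| Scores used | r | v | Detectable d | Power at 0.33 | Power at 0.8 |
|---|---|---|---|---|---|
| 1 pre, 1 post | 0.5 | 0.750 | 0.92 | 17% | 68% |
| 1 pre, 1 post | 0.7 | 0.510 | 0.76 | 23% | 84% |
| 1 pre, 1 post | 0.8 | 0.360 | 0.64 | 31% | 94% |
| 2 pre, 2 post | 0.5 | 0.417 | 0.68 | 27% | 91% |
| 2 pre, 2 post | 0.7 | 0.274 | 0.55 | 39% | 98% |
| 2 pre, 2 post | 0.8 | 0.189 | 0.46 | 52% | over 99% |

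A detectable d of 0.33 requires r of about 0.95 in the first layout and 0.90 in the second. Adding T0 as a third pre-score lowers this to about 0.88, for the three measures collected then.

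**4. Within-condition change.** If d is read as the standardised T1-T4 change in one arm (paired test, n = 15), power at 0.33 is 22.2%. For all 45 pooled it is 58.1%.

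**5. Precision.** The unadjusted 95% confidence interval for a between-arm difference has half-width t(42)·√(2/15) = 2.018 × 0.365 = 0.74 SD.

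**The case against.** The strongest reply is that this is a feasibility pilot. The primary aim is feasibility, 45 is first justified by what can be recruited, Aim 3 is described as exploratory and as an initial estimate, and full power is left to Phase III. No decision rule depends on the sentence, and nothing in the protocol plans to read a null result as no effect. All of this stands and limits the severity. It does not make the stated figure true.

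A second reply is that the plan includes mixed models, so the t-test is a worst case. This also stands. A reader might infer that the trial has 80% power only at d of about 1.06 and would miss d = 0.8 almost half the time. That holds only for the unadjusted t-test; with adjustment, power at 0.8 runs from about 68% to over 99% under the assumed correlations. Adjustment still does not bring the detectable effect to 0.33 at those correlations.

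A third temptation is to conclude that the sponsor powered a time effect pooled over arms, which with five visits would include the gain from the memory group before randomisation. The protocol does not name the test, and some interaction set-ups, which do compare arms, give the same number. The pooled time effect is one possibility, not a finding. Nor can an interaction f be doubled and quoted as a between-arm d, in either direction of the argument.

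**Conclusion.** The statement is wrong as a between-arm standardised difference with 15 per arm. The detectable effect at 80% power is about 1.06 unadjusted. Adjusted, it is about 0.92 to 0.64 with one pre-score and one follow-up and about 0.68 to 0.46 with two of each, for correlations of 0.5 to 0.8. These figures rest on two-sided 5%, 80% power, compound symmetry, no attrition and randomisation after T2. Only a correlation of about 0.9 or more would rescue 0.33, and the protocol claims none.

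The source of 0.33 remains unidentified. The defect is an unsupported detectability statement, not a failure to power a pilot. It should be fixed, but it does not threaten the trial's conduct or its primary aim.

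**What to change.** In the Sample size section, either delete the d = 0.33 claim and its comparison with earlier booster effects, or restate it with its test, alpha, power, number of measurements and correlation, and say that it is not a between-arm difference.

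Rest the choice of 45 on the recruitment and feasibility grounds already given. Add what 15 per arm delivers between arms: an unadjusted 95% confidence-interval half-width of about 0.74 SD, and a detectable d of about 1.06 unadjusted and about 0.5 to 0.9 adjusted, with the correlation assumptions stated.

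Under Aim 3, say that a non-significant difference will not be read as absence of effect.

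The cost is protocol wording only, with no extra participants. The stated figure becomes less favourable.

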 - b. The number of available and eligible potential participants and rates of recruitment

- c. The willingness of participants to be randomised
 - d. The appropriateness of the proposed set of outcome measures
 - e. Rates of adherence and compliance to follow-up assessments
 - f. The time required to collect and analyse data
3. Provide an initial estimate of the extent to which the two eHealth interventions maintain benefits from memory rehabilitation compared with no active maintenance, measured over an 18-week period; and
 4. Estimate the potential cost and cost-effectiveness of delivering the proposed maintenance intervention program (i.e. booster sessions and SMS reminders) compared with no active maintenance.

Ultimately, we will use the information from all four of these aims to estimate the parameters for a Phase III trial.

Hypotheses

We hypothesise that the level of everyday memory function at the end of the study, from largest to smallest effect, will be: eHealth booster sessions > SMS/Email reminders > no active maintenance.

STUDY DESIGN

Research Design

We will conduct a multi-site, single-blind, Phase II pilot randomised controlled trial (RCT) with three arms to evaluate two eHealth interventions designed to sustain the effects of memory skills training (booster sessions delivered via videoconferencing, and SMS/email reminders) compared to no active maintenance. We will use an intention to treat method of analysis, as well evaluate the maintenance interventions as per protocol in terms of:

- 1) Feasibility;
- 2) Effectiveness in prolonging intervention-related gains; and
- 3) Estimated cost.

PARTICIPANTS

Recruitment Procedure

Potential participants will be identified from survivors of stroke enrolled to participate in a memory skills group program at one of the health service sites participating in the study (please see Study Sites section). These sites are already running, or are planning to run, memory skills groups as part of usual care.

Recruitment will follow a two-step process:

1. Prior to commencing the memory skills group program, willingness to participate in the Memory-SuSTAIN study will be established. Health service staff will obtain verbal consent for identified potential Memory-SuSTAIN participants to be contacted by study staff to discuss participation.

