2. At the conclusion of the memory skills group program, interested participants will be re-contacted by study staff to be formally enrolled in the Memory-SuSTAIN study. The initial outcome assessment data (T1) will then be collected within three weeks of completion of the memory group program (completion is defined as minimum attendance of four out of the six total weekly group sessions). Randomisation (1:1:1) will occur once participants are formally enrolled in the study.

A flyer will also be distributed to memory group participants inviting expressions of interest.

Inclusion Criteria

Participants will satisfy the following criteria:

1. Adults (age at least 18 years);
2. Primary diagnosis of stroke as determined by medical records;
3. At least 3 months post-stroke;
4. Everyday memory complaints, reported by self or other;
5. Sufficient cognitive and English language skills to participate in a memory skills group;
6. Completion of a memory skills group program at any of the participating clinical sites (defined as attending at least 4 of the 6 memory group sessions);
7. Access to a computer with a webcam and internet connection; and

8. Access to either SMS text messaging via a mobile phone with active service, or an active email service.

Exclusion Criteria

1. Severe psychiatric illness
2. Known presence of a neurodegenerative conditions (e.g. dementia), severe mental health conditions, or other known neurological disorder impacting cognition
3. Major illness and unlikely to survive up to final follow-up assessment
4. Current participation in other individual rehabilitation sessions focusing on memory or other cognitive functions.

Consent

Eligible participants will be provided with a verbal explanation of the study requirements and a participant information statement. Participants will be required to provide written consent before enrolment to the study. Consent forms will be stored securely at La Trobe University in individual client paper files (please see Data Handling and Security section below). The Participant Information and Consent Form (see attachment) will explain the following:

- What information is being collected
- Voluntary participation and withdrawal rights
- The purposes for which the information is being collected
- The period for which the records relating to the participant will be kept
- The form in which the data will be stored (i.e. whether identifiable or not)

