- The steps taken to ensure confidentiality and secure storage of data
- How privacy and confidentiality will be protected in any publication of the information
- The fact that the individual may access that information
- Any risks and benefits from participation

Group Randomisation and Blinding

[figure not shown]
Participants will be randomised into one of three groups:

- 1) Receiving 3 x 1-hour booster sessions over a period of 6 weeks
- 2) Receiving a minimum of 6 x SMS/email strategy reminders over a period of 6 weeks

3) No active maintenance.

The randomisation sequence will be generated by the Research Officer using Stata Version 15 (StataCorp, 2017). The sequence will be generated using random block sizes with 6 allocations per block (2 per condition), stratified by health service site to ensure equal distribution across sites. The randomisation schedule will then be uploaded to REDCap, which will ensure allocation concealment. As participants complete their post-break assessment (i.e. the T2/12-week outcome assessment, see flowchart below), the Memory-SuSTAIN study Research Officer will trigger randomisation within REDCap and inform both participants and the relevant team members delivering the maintenance interventions (i.e. those arranging SMS/Email reminders or conducting booster sessions) of the participant allocations.

PARTICIPANT FLOWCHART

MAINTENANCE INTERVENTION

Participants will be contacted following the 12-week assessment by the Memory-SuSTAIN research officer and informed of their random group allocation.

Maintenance Program option 1: Telehealth booster sessions

Participants in the Booster Sessions condition will receive three fortnightly sessions of one-hour duration each, with a trained clinician. Sessions comprise:

- Checking the progress of rehabilitation goals (previously negotiated with memory group clinicians);
- Reviewing and consolidating key compensatory and lifestyle strategies covered during the memory group program;
- Expanding the number and range of everyday situations to which these memory strategies could be applied; and
- Addressing any barriers to ongoing implementation of strategies.

Booster sessions will occur remotely via videoconferencing using Zoom, a freely available software program facilitating Internet-enabled videoconferencing. Booster sessions will also be video recorded and treatment fidelity checks conducted by an independent expert.

Maintenance Program option 2: SMS/Email Reminders

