- Frequency of technical issues (e.g., message send failures, internet dropouts during telehealth sessions).
- The time required to collect data.
- The feasibility of data collection related to costs will be assessed by accessing the amount of missing data and participants opting out of providing these data.

Measures for Aim 3 (*Determining an initial estimate of intervention effectiveness*):

1) Goal Attainment Scaling (GAS; Turner-Stokes, Williams, & Johnson, 2009)

GAS is a person-centred measure of rehabilitation progress commonly used with clinical populations, to define and assess attainment of therapy goals. Participants will be invited to nominate two problematic types of memory lapses in everyday activities, in which improvements would represent realistic participation goals.

2) Everyday Memory Questionnaire-Revised (EMQ-R; Royle & Lincoln, 2008)

Self-reported lapses in memory will be assessed using the Everyday Memory Questionnaire-Revised, a 13-item item scale measure of memory failures in everyday activities.

3) Strategy Use Checklist

A self-report Strategy Use Checklist will record participant use of external strategies (e.g., lists, smartphone applications) and internal strategies (e.g., mental rehearsal, face-name association) from “Daily” to “Not at all”.

4) Rivermead Behavioural Memory Test – Third edition (RBMT-3; Malec, Zweber, & Depompolo, 1990)

Everyday memory will be assessed via the RBMT, an ecologically valid measure of functional performance in everyday tasks. 14 subtests cover verbal, visual, recognition, recall, immediate, and delayed memory performance. Items include demonstrating recall of a route around a room, recalling the locations of objects in the room, and recognising a series of faces.

5) The Valued Living Questionnaire (VLQ; Wilson, Sandoz, Kitchens, & Roberts, 2010)

As a brief self-report measure of quality of life from a behavioural perspective, the VLQ captures the extent to which participants’ actions are consistent with their values or the areas during the previous week.

6) Community Integration Questionnaire (CIQ; Willer, Ottenbacher, & Coad, 1994)

The CIQ is a 15-item self-report measure of social role limitation and community participation. Items include “approximately how many times do you participate in leisure activities such as movies, sports, restaurants, etc”.

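### Aim 3 compares the arms at visits that precede allocation, and measures each condition's effect from T1, six weeks before treatment can differ

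*Protocol*

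**What the plan says.** **Allocation and treatment.** Group Randomisation and Blinding states: "As participants complete their post-break assessment (i.e. the T2/12-week outcome assessment, see flowchart below), the Memory-SuSTAIN study Research Officer will trigger randomisation within REDCap". The Maintenance Intervention section has participants told their allocation after the 12-week assessment, and its No Active Maintenance paragraph places the intervention phase between T2 and T3. Recruitment Procedure gives a different time: "Randomisation (1:1:1) will occur once participants are formally enrolled in the study", with enrolment at the end of the memory skills group.

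**Visits.** The Memory Skills Group Sites section calls T0 the baseline, with the first three Aim 3 measures only. It lists T1 (week 6), T2 (week 12), T3 (week 18) and T4 (week 24) together as outcome assessments.

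**Analysis.** For Aim 3: "Pairwise comparisons and linear mixed models will be used to explore between-group differences at each time point in clinical outcomes". The next sentence continues: "The effect size of each maintenance condition, defined as the magnitude of change from T1-T4", estimated as Cohen's d from regression output. Aim 1, in the same section, limits its group comparisons to T3 and T4.

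**Hypothesis.** "We hypothesise that the level of everyday memory function at the end of the study" will be ordered booster, then reminders, then no active maintenance. Measures for Aim 3 offers two measures that fit: the EMQ-R, on self-reported everyday lapses, and the RBMT-3 ("Everyday memory will be assessed via the RBMT").

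**The concern.** No participant is treated differently by arm until T2 is complete, so a group difference at T1 or T2 is chance. The Aim 3 wording still puts those visits on the same footing as T3 and T4. With 15 per arm, chance imbalances can be sizeable and could be reported as findings.

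The effect-size definition raises a second problem. It attaches T1-to-T4 change to each condition, although that window opens six weeks before the condition begins. The Background expects gains from memory training to fade. Fading between T1 and T2 would enter every condition's d, and the Aims section says the results will supply parameters for a Phase III trial.

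Third, T2 is the last untreated score and the natural baseline. Using it as one more outcome gives up precision that the data already collected could provide.

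**Working it through.** **1. Count of comparisons.** Inputs: six Aim 3 measures; three of them at T0; all six at each of T1–T4 (assumed, since the flowchart is not shown); three arms, hence three pairs.

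- T1 and T2: 6 × 2 × 3 = 36
- T3 and T4: 6 × 2 × 3 = 36
- Share over the visits labelled outcome assessments: 36/72 = 50%
- With T0 counted: (3 + 6 + 6) × 3 = 45 of 81 = 56%

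The protocol states no significance level. At an assumed 5%, the early comparisons would give 36 × 0.05 = 1.8 false positives on average (45 × 0.05 = 2.25 with T0).

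**2. Dependence on the time of randomisation.** Under Group Randomisation and Blinding, T1 and T2 both precede allocation. Under Recruitment Procedure, T2 falls after allocation. If T1 is still taken as before it, the share preceding allocation is 18/72 = 25%, or 27/81 = 33% with T0. On either version T1 and T2 precede treatment, so neither can show its effect.

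**3. What the per-condition d contains.** For one arm:

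mean(T4) − mean(T1) = [mean(T2) − mean(T1)] + [mean(T4) − mean(T2)]

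The first bracket covers weeks 6–12, which is 6 of 18 weeks (one third), and is untreated in every arm. It has the same expectation in all arms. It therefore cancels when one arm's change is subtracted from another's, but it stays in each arm's own d.

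**4. Precision of the between-arm contrast at T4.** The protocol gives no SD or correlation, so variances are in units of a common σ². The comparator, raw T4−T1 change, is also an assumption, because the protocol says only that d comes from regression output.

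Exchangeable correlation ρ:

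- T4−T1 change: 2(1 − ρ). This equals the T4−T2 variance, so moving the anchor alone gains nothing.
- T4 adjusted for T2: 1 − ρ²
- T4 adjusted for T1 and T2: 1 − 2ρ²/(1 + ρ)
- ρ = 0.5: 1.00, 0.75 and 0.667, reductions of 25% and 33%
- ρ = 0.8: 0.40, 0.36 and 0.289, reductions of 10% and 28%

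Serial decay, correlation r per six weeks:

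- T4−T1 change: 2(1 − r³)
- T4−T2 change: 2(1 − r²)
- T4 adjusted for T2: 1 − r⁴
- r = 0.7: 1.314, 1.020 and 0.760, total reduction 1 − 0.760/1.314 = 42%
- r = 0.9: 0.542, 0.380 and 0.344, total reduction 1 − 0.344/0.542 = 37%

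Under decay the total mixes two gains. The anchor part alone is the ratio (1 − r³)/(1 − r²): T1-anchored variance is 1.29 times T2-anchored at r = 0.7 and 1.43 times at r = 0.9.

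**5. Comparisons that bear on the hypothesis.** It concerns the end of the study: two candidate measures × T4 × three pairs = 6.

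**The case against.** The T1 start looks deliberate. The Aims section asks how well benefits are maintained over 18 weeks, which is exactly week 6 to week 24, and T1 is the level to be maintained. That stands, and T1-to-T4 change is a sound description of maintenance within an arm. It does not make that change the effect of a condition that starts at T2.

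Early visits may properly sit in a mixed model if arm means are constrained equal there, and an analysis plan not shown might say so. But the protocol itself commits to group comparisons at every time point, and Aim 1 shows that its authors could restrict visits. Aim 3 is exploratory in a pilot whose primary aim is feasibility, which lowers the stakes to interpretation and planning values.

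Four stronger readings are tempting and not supported:

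- That more than half of the comparisons are empty. This needs T0 counted as an outcome, whereas the protocol calls it baseline; over its outcome visits the share is exactly half.
- That starting at T1 always adds noise. Under exchangeable correlation it adds none, and the gain comes wholly from covariate adjustment.
- That starting at T1 biases the comparison of arms. The T1–T2 change cancels in expectation.
- That any of 36 later comparisons could be used to claim the hypothesis, with up to an 84% chance of a false positive (1 − 0.95³⁶). The hypothesis fixes the end of the study, which leaves about 6, or 26% on the same independence and 5% assumptions. It also predicts a full ordering of three arms, which one favourable pair would not establish.

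**Conclusion.** The point holds in limited form and is worth correcting. Half of the Aim 3 comparisons over the protocol's own outcome visits (36 of 72, assuming all six measures at each visit) precede any difference in treatment and cannot show an effect. Each condition's d carries six untreated weeks out of 18. That misattributes any change in those weeks to the condition, while leaving the between-arm contrast unbiased.

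Adjusting T4 for T2 would reduce variance by roughly 10–42% against raw T4−T1 change, across the assumed correlation patterns. The size rests on those assumptions; the direction does not depend on which pattern is chosen.

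The two statements on the time of randomisation conflict. The conclusion survives either, because T2 is untreated on both.

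**What to change.** - Limit between-arm contrasts and the between-arm effect size for Aim 3 to T3 and T4. Adjust for the T2 score (T1 may be added) and for site, the stratification factor. To much the same effect, fit a mixed model with arm means constrained equal before allocation.
- Tabulate T0, T1 and T2 by arm without between-group tests.
- Keep T1-to-T4 change, if wanted, as a within-arm description of maintenance and not as the effect of a condition.
- Reconcile Recruitment Procedure with Group Randomisation and Blinding on when randomisation occurs.
- Secondary: state that the hypothesis is judged on the EMQ-R at T4. This agrees with the primary objective in the synopsis, which is about everyday memory as participants report it.

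The cost is a change of wording and a few degrees of freedom for site (four with the five listed sites). No new data are needed.
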